A comparison of Mepitel Ag vs antibiotic ointment when used with a soft cast technique for the treatment of pediatric hand and foot burns, a prospective study

Protocol #: 15-1828

April 8, 2016

COMIRB Protocol

COLORADO MULTIPLE INSTITUTIONAL REVIEWBOARD
[name] [contact] [contact]

Protocol #: 15-1828

Project Title: A comparison of Mepitel Ag vs antibiotic ointment when used with a soft cast technique for the treatment of pediatric hand and foot burns, a prospective study

Principal Investigator: [name], MD

Version Date: 3/30/16

- I. **Hypotheses:** Mepitel Ag in combination with the soft cast technique improves wound healing in pediatric partial to deep partial thickness hand and foot burns by decreasing the length of healing time, decreasing the risk of yeast infection, and decreasing pain associated with multiple dressing changes.
- II. **Specific Aims:**
 - 1) To examine the efficacy of Mepitel Ag for use in pediatric partial to deep partial thickness hand and foot burns.
 - 2) To evaluate Mepitel Ag to triple antibiotic ointment when used in combination with a soft cast technique comparing healing time, yeast infection rates and pain levels at time of dressing change.

II. Background and Significance:

There is currently no gold standard dressing when it comes to treating hand or foot burns, specifically in the pediatric population. Our institution currently utilizes a soft cast technique (SCT) on all of our hand and foot burns. The SCT provides optimal positioning of the wounded hand or foot, allows for a moist wound environment, and offers protection of the injured extremity as the wound heals. Our current SCT uses triple antibiotic ointment (TAO) impregnated Adaptic gauze, kling or kerlex, cast padding, gypsoma plaster, soft cast material, and coban. This dressing is applied two to three times during the first 2 weeks post injury. To reduce the risk of the development of yeast overgrowth, the underlying dressing is changed to nystatin impregnated Adaptic gauze, kling or kerlex, cast padding, gypsoma plaster, soft cast material, and coban for the remainder of treatment time or until OR is indicated for surgical debridement and grafting of wounds..

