This is due to the fact that “soft silicone dressing have been shown to prevent trauma to the wound bed and periwound skin and have been described as ‘atraumatic’”.¹⁴ Other benefits of soft silicone dressings include the ability to conform to anatomical contours, a reduction in scar development, and reduced overall cost secondary to improved wound healing and need for less frequent dressing changes.¹⁴

Mepitel Ag, a hybrid type soft silicone dressing impregnated with a silver compound was recently approved for use in partial thickness burns and partial and full thickness grafts.¹⁵ This combination of soft silicone and silver provides a relatively pain free dressing with broad spectrum antibiotic coverage. The aim of this study is to demonstrate that Mepitel Ag in combination with a soft cast technique is a superior alternative to antibiotic ointment impregnated gauze and soft cast for the treatment of pediatric hand and foot burns due to decreased healing time, decreased patient pain and lower yeast infection rates.

IV. Research Methods

A. Outcome Measure(s):

Primary outcomes utilized in this study include overall wound outcome, measured in length of days to re-epithelialization or need for surgical intervention, clinical assessment and wound progression photographs. Secondary outcomes include number of patients requiring surgical debridement, presence of infection based on odor, rash, deep red appearance or puritis. These wounds will not be cultured, patient pain level with dressing change based on the FLACC (Face, Legs, Activity, Cry, Consolability) scale, parents perceived level of pain, pain level at home based on family reported pain and pain medication use. We will also assess cost effectiveness of dressings including the number of clinic visits, number of soft casts, and the cost and amount of dressings used over the course of treatment.

B. Description of Population to be Enrolled:

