
brown or black in color, dry appearing; 10) Fourth degree- third degree + muscle and or bone involvement. The provider and burn nurse will each give the patient a number and the severity will be determined based on the average of the 2 numbers. Any patient given a number 2, 3 or 4, will be placed into the "partial thickness" category, any patient given a 5, 6, or 7 will be placed into the "deep partial thickness" category, and lastly, any patient given an 8 or 9 will be placed into the "full thickness" category for burn severity.

Patients will be randomized into one of two groups, Mepitel Ag or standard TAO, using RedCap and based on a random clinical trial excel spread sheet balanced by burn severity. A statistician will provide a randomization scheme for investigators to follow. Photographs will be taken prior to dressing application at the initial visit and each subsequent visit. ~~Patient wounds will be dressed in either Mepitel Ag, kling or kerlex, cast padding, gypsoma plaster, soft cast material and coban for up to 21 days or until complete re-epithelialization of the wound occurs or unless surgery is indicated; the control, standard dressing of Triple Antibiotic Ointment impregnated adaptic gauze, kling or kerlex, cast padding, gypsoma plaster, soft cast material and coban for 10-14 days, or Nystatin impregnated adaptic, kling or kerlex, cast padding, gypsoma plaster, soft cast material and coban for 8-21 days or until complete re-epithelialization of the wound occurs or surgery is indicated. The SCT is applied by Occupational and Physical trained in casting and positioning. The soft cast provides optimal positioning while eliminating friction on the burn area. Dressing changes will occur every 3-10 days and will be determined by the provider, based on burn wound severity. Upon each return clinic visit, the patient will have their wound severity assessed by the following scoring system: 1=0% healed, 2=20% healed; 3=40% healed; 4=60% healed; 5=80% healed; 6=100% healed. This will be established by provider and burn nurse examination of the wound. This will be recorded in RedCap:_____~~

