Analysis Plan: Demographic and clinical characteristics will be summarized and compared between the two treatment groups using chi-squared and two-sample t-tests for categorical and continuous data, respectively. For analysis of the primary outcome, time to wound healing, we will use Kaplan-Meier curves, the log-rank test and a Cox proportional hazards model to determine the difference in days to re-epithelialization between the TAO and Mepitel Ag soft cast methods. Patients that require surgical intervention will be censored at the time of surgery. Logistic regression will be used to analyze the secondary outcomes, need for surgical debridement and occurrence of yeast infection. Pain level outcomes and pain medication use will be compared using two-sample t-tests and chi-squared tests. Cost effectiveness outcomes will also be analyzed.

1. Sample size: A statistical power analysis was performed to estimate power, based on results reported in A Soft casting Technique to Manage Pediatric Hand Burns: Less Pain, Greater Gain.²² Considering the simplest between group comparison and assuming a standard deviation of 0.3, alpha of 0.05 and 50 subjects per group there is over 90% power to detect a difference of 2 days between the treatment groups. Thus, we expect that our proposed sample size of 100 burns will be adequate for the main objective of this study.

G. Summarize Knowledge to be Gained:

To demonstrate that Mepitel Ag in combination with a soft cast technique improves wound healing in pediatric partial to deep partial thickness hand and foot burns by decreasing the length of healing time, decreasing the risk of yeast infection, and decreasing pain associated with dressing changes.

H. References:

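### The cost-effectiveness outcome names no surgical resource use, so cost may be understated in the arm with more surgery, and that arm can look cheaper if surgery cuts dressing short

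*Combined protocol and SAP*

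**What the plan says.** Section IV.A says the team will look at "cost effectiveness of dressings including the number of clinic visits, number of soft casts, and the cost and amount of dressings used", with the treatment course as the period covered. No operation, graft, theatre or post-operative item is named. Surgery appears in the same section only as a separate outcome: "Secondary outcomes include number of patients requiring surgical debridement".

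The nursing questionnaire described in IV.C records the type and amount of product used at each dressing change. It has no surgical resource item. Section IV.F gives the whole cost analysis in one sentence: "Cost effectiveness outcomes will also be analyzed". It states no unit costs, time horizon, measure of effect or rule for burns that go to surgery.

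On when dressing ends, IV.C says that Mepitel Ag is used "for up to 21 days or until complete re-epithelialization of the wound occurs or unless surgery is indicated" and that the nystatin phase of the control dressing runs "for 8-21 days or until complete re-epithelialization of the wound occurs or surgery is indicated". In the extracted text these sentences carry strike-through marks, so their status is uncertain. Background and Significance carries no such marks. It says of the institution's current practice that dressing continues "for the remainder of treatment time or until OR is indicated for surgical debridement and grafting of wounds".

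**The concern.** Surgery is a foreseeable result of failed healing in this trial. Section IV.B admits full thickness burns, level 7 of the severity scale in IV.C anticipates a possible graft, and surgical debridement is a secondary outcome. An operation is likely to be the most expensive event in a burn's course, yet it is not among the named cost items. The same event also ends the accrual of study dressings and soft casts.

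A cost comparison that keeps to the named items would therefore omit a main cost of treatment failure, and could record that failure as lower dressing use. Section III cites lower overall cost through better healing as a benefit of soft silicone dressings. A list without surgery cannot test that benefit for the burns that fail to heal.

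**Working it through.** The plan states no cost, unit cost or surgery rate, so there is no figure to reproduce. The check asks only in which direction the named items move when surgery is left out, using soft casts as the example.

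**One simple case (all figures assumed).** A healed burn uses 4 casts, a surgical burn uses 2 before stopping, and surgery occurs in 10% of one arm and 30% of the other.
- Mean casts, 10% surgery: 0.9 × 4 + 0.1 × 2 = 3.8
- Mean casts, 30% surgery: 0.7 × 4 + 0.3 × 2 = 3.4
- Ratio: 3.4 / 3.8 = 0.895, so the arm with more surgery looks 10.5% cheaper on casts
- Extra operations per 50 burns: 50 × (0.30 − 0.10) = 10, none of them costed
- The saving disappears once an operation costs more than 0.4 / 0.2 = 2 casts

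The 2-cast gap favours the concern. Background and Significance gives two to three applications in the first 2 weeks, and a cast may stay on for 7-10 days. If the gap is 1 cast, the difference is 0.2 × 1 = 0.2 casts; if it is 0, there is none.

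**A range of timings.**
- From the documents: change intervals of 3, 7 and 10 days. The 3-10 day range is in the strike-through text of IV.C; 7-10 days is in Background and Significance.
- Assumed: surgery in 10% of arm A and 20% of arm B; surgery on day 7, 10, 14 or 21; other burns healed on day 14 or 21.
- Casts used to day T at interval g: the quotient T/g rounded up. For days 7, 10, 14 and 21 this gives 3, 4, 5, 7 (g = 3); 1, 2, 2, 3 (g = 7); and 1, 1, 2, 3 (g = 10).
- Difference B − A in mean casts per burn: (0.20 − 0.10) × (casts to surgery − casts to healing).

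| Interval (days) | Healing day | Surgery day 7 | Day 10 | Day 14 | Day 21 |
|---|---|---|---|---|---|
| 3 | 14 | −0.2 | −0.1 | 0 | +0.2 |
| 7 | 14 | −0.1 | 0 | 0 | +0.1 |
| 10 | 14 | −0.1 | −0.1 | 0 | +0.1 |
| 3 | 21 | −0.4 | −0.3 | −0.2 | 0 |
| 7 | 21 | −0.2 | −0.1 | −0.1 | 0 |
| 10 | 21 | −0.2 | −0.2 | −0.1 | 0 |

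Of the 24 cells, 14 are negative, 7 are zero and 3 are positive. Surgery precedes healing in 15 cells: 14 show fewer casts in the arm with more surgery and 1 is a tie. The 3 positive cells all have surgery on day 21 against healing on day 14.

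**Adding the operation.** If an operation costs C cast-equivalents, the difference becomes (table value) + 0.10 × C. In the 14 negative cells the apparent saving is gone once C exceeds 1 to 4.

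**Earlier surgery alone.** Take 20% surgery in both arms, on day 7 in one and day 14 in the other. The earlier arm's count changes by 0.2 × (3 − 5) = −0.4 at a 3-day interval, and by 0.2 × (1 − 2) = −0.2 at 7 or 10 days.

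**The case against.** A reader might infer that the plan excludes surgery or sets its cost at zero. It does neither. The list in IV.A is introduced by *including*, so it is open, and the plan is silent on surgical cost.

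A reader might also infer that every named item stops accruing at surgery. The documents do not support that. What ends is the dressing course; no section ends clinic visits at surgery. The stated horizon, the course of treatment, could take in post-operative visits and dressings, which might offset the shortfall. For the Mepitel Ag arm, even the stopping of dressings rests on the strike-through text, because the unmarked statement in Background and Significance covers only current practice.

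The strongest inference would be that an arm with more surgery always looks cheaper. The table shows otherwise: late surgery after a long dressing course reverses the sign.

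Finally, surgery has its own logistic regression in IV.F, so an imbalance would be reported, and cost appears in neither the hypotheses nor the specific aims.

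All of this stands, and it limits the point. It does not remove it. Nothing in the plan commits the team to counting surgery or says how far the cost horizon runs, and reporting surgery separately does not bring it into the cost result.

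**Conclusion.** The point holds as a minor one. No surgical resource use is named, collected by the questionnaire or provided for in the analysis. If the comparison keeps to the named items, cost is understated more in the arm with more surgery. Whether that arm then looks cheaper depends on timing: it can when surgery comes before those burns would otherwise have finished dressing.

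In the assumed scenarios with 10 percentage points more surgery, the effect ran from 0.4 fewer to 0.2 more casts per burn. The 3.8 versus 3.4 example is a single assumed scenario. These sizes rest on assumed surgery rates and timings, on dressing ending at surgery in both arms, and on post-operative visits and dressings not being counted. The direction is therefore possible, not established.

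**What to change.** In IV.A and IV.F, count each surgical debridement or graft, at one fixed unit cost or at hospital charges, as resource use for the arm to which the burn was randomised. Count post-operative visits and dressings until wound closure in the same way. Analyse all randomised burns, and show the mean cost difference between arms beside the surgery rate in each arm. I would not divide each arm's total cost by its number of healed burns: that gives an average for each arm, not a comparison between them.

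If only the named items are kept, call the result a dressing-use comparison and make no cost-effectiveness claim.

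The first option costs a few lines of text and a unit cost; surgery is already an outcome. Its downside is that post-operative use must be pulled from the hospital record, because the questionnaire does not capture it. Since each injured extremity is a separate data point (IV.B), the text should also say how a visit or operation shared by two burns in one child is split. The second option costs only the relabelling.

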Patients to be included in this study will be all Children's Hospital Colorado burn patients between the ages of 31 days and 18 years with newly diagnosed partial to deep partial or full thickness hand or foot burns, including bilateral or unilateral injury. Each injured extremity will serve as a separate data point. Exclusions include age > 18 years at start of study, silver allergy, silicone allergy, electrical or chemical burn, past medical history of immunodeficiency disorders such as diabetes mellitus, AIDs, or HIV, pregnant women, prisoners children under the protection of the department of human services, and the decisionally challenged.

C. Study Design and Research Methods

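### The hypothesis, Aim 1 and the planned conclusion name partial to deep partial burns, but full-thickness burns are randomised and the primary analysis sets no depth restriction or stratification

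*Combined protocol and SAP*

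**What the plan says.** The texts that define the research question do not agree on burn depth.

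- **Section I, Hypotheses:** the dressing "improves wound healing in pediatric partial to deep partial thickness hand and foot burns by decreasing the length of healing time". The end of the background section repeats this, and IV.G words the knowledge to be gained for the same depths.
- **Specific Aim 1:** "To examine the efficacy of Mepitel Ag for use in pediatric partial to deep partial thickness hand and foot burns".
- **Specific Aim 2:** "To evaluate Mepitel Ag to triple antibiotic ointment when used in combination with a soft cast technique", with no depth given. The title names no depth either, nor does the aim at the end of section III, which is worded "for the treatment of pediatric hand and foot burns due to decreased healing time, decreased patient pain and lower yeast infection rates".

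The texts that define who is studied are wider.

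- **IV.B** enrols "newly diagnosed partial to deep partial or full thickness hand or foot burns", and IV.C randomises the same range.
- **IV.C** averages two raters' scores on a 10-point scale. Scores 2-4 are partial thickness, 5-7 deep partial and 8-9 full thickness. Allocation is to be balanced by severity.

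**IV.F** specifies Kaplan-Meier curves, a log-rank test and a Cox model for days to re-epithelialization. It mentions no restriction, stratum, covariate or subgroup by depth. It adds: "Patients that require surgical intervention will be censored at the time of surgery".

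**The concern.** If IV.F is followed as written, every randomised burn enters the primary test, and IV.G then words the result for two of the three severity categories. A reader of the result could not tell whether it describes the named depths or the mixture.

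Full-thickness burns also behave differently in this analysis. IV.C already notes that a score-7 burn may need a graft, and scores 8-9 are deeper. Such burns are likely to be censored at surgery or to heal slowly. They fill places among the 100 burns and add few healing events. Until surgery they sit in the risk sets of both arms, which can dilute an unstratified comparison.

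**Working it through.** **1. The plan's own figure.** Inputs from IV.F: difference 2 days, SD 0.3, alpha 0.05, 50 per group. The standard error is 0.3 × √(2/50) = 0.06, and 2/0.06 = 33.3, so power is close to 100%. The statement of over 90% is therefore true as calculated. If only 60 burns (30 per group) were of the named depths, the standard error would be 0.3 × √(2/30) = 0.077, and 2/0.077 is about 26. Power is still close to 100%. At this SD the depth mix does not move the stated power.

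**2. Share of healing events from full-thickness burns.** The documents give no depth mix and no surgery rate, so these inputs are assumptions: a fraction f of the 100 burns is full thickness (10-30%), a fraction h of those heals without surgery (10-40%), and 90% of the others heal without surgery.

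- Events in the named depths = 100 × (1 − f) × 0.9
- Events in full thickness = 100 × f × h
- Loss from restricting = full-thickness events / all events

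| f | h | Named depths | Full thickness | Loss |
|---|---|---|---|---|
| 10% | 10% | 81 | 1 | 1.2% |
| 10% | 40% | 81 | 4 | 4.7% |
| 30% | 10% | 63 | 3 | 4.5% |
| 30% | 40% | 63 | 12 | 16.0% |

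On these assumptions full-thickness burns are 10-30% of the sample but supply 1.2-16% of the healing events.

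**3. Dilution if the benefit is confined to the named depths.** Suppose the 2-day benefit is zero in full thickness. The pooled difference is 2 × (1 − f), or 1.8, 1.6 and 1.4 days at f = 10, 20 and 30%. To see an effect on power, an SD other than 0.3 is needed. Take 2 / [√(2/50) × (1.960 + 1.282)] = 3.085 days, the largest SD that gives 90% power with 50 per group. This is an assumption, not a figure in the plan.

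| f | Pooled, all 100 burns | Named depths only |
|---|---|---|
| 10% | 83.1% | 86.8% (90 burns) |
| 20% | 73.7% | 82.6% (80 burns) |
| 30% | 62.1% | 77.4% (70 burns) |

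**4. Simulated log-rank test.** All inputs are assumed:

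- 100 burns, 20% full thickness, and a hazard ratio of 1.92 at every depth (this gives 90.3% power with 100 events);
- control median healing of 12 days in the named depths and 20-35 days in full thickness;
- 10% of named-depth burns facing surgery at days 7-14;
- full-thickness surgery at times varied from days 5-12 to days 10-35.

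Power was 26-79% pooled and unstratified, 78-80% for the named depths alone, and 80-85% pooled but stratified by severity. A second set, with a full-thickness hazard ratio of 1.92 or 1.0, gave about 19-78%, 78-79% and 75-83%.

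The low ends need slow full-thickness healing, late surgery and a healing hazard that rises over time. With early surgery and a common hazard ratio the three analyses nearly coincide. With a constant healing hazard and a common hazard ratio, pooling costs little.

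**The case against.** Several stronger readings are tempting, and the documents do not support them.

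- **That a different population is tested.** The named depths are a subset of those randomised, so the tested population is broader. The event shares in step 2 also mean that 84-99% of healing events would come from the named depths. It would be too strong to say that the pooled hazard ratio is uninformative about them.
- **That both aims are limited by depth.** Aim 2, the comparative aim, is not. It already fits the enrolled population, as do the title and the section III aim.
- **That the plan says it pools all depths.** No sentence says so. IV.F lists no Cox covariates and does not say whether the log-rank test is stratified. Pooling is the natural reading of that silence, but it is an inference.
- **That the mismatch undermines the stated power.** Step 1 shows that it does not. The SD of 0.3 is a separate matter.
- **That enrolment contradicts the approved use.** Section III describes the dressing as "recently approved for use in partial thickness burns and partial and full thickness grafts". This is background taken from a product source, and enrolling beyond a quoted indication is not an internal contradiction. Section III also says that other silver products are indicated for partial to full thickness wounds, which gives some rationale for including deeper burns.

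Restriction is also not free of difficulty. An averaged score of 7.5 falls in no category, and score 7 already includes areas of full thickness. IV.C scores the patient while IV.B counts each extremity, so bilateral burns of unequal depth need a rule before the restricted comparison is clearly a randomised one. These points bear on the choice and wording of the fix. They do not reconcile the hypothesis, Aim 1 and IV.G with IV.B, IV.C and IV.F.

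**Conclusion.** The inconsistency is in the current text and should be corrected before analysis. The hypothesis, Aim 1 and IV.G name two depth categories. Enrolment and randomisation cover three, and IV.F says nothing that isolates the two. The conclusion as planned would be narrower than the population tested.

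The size cannot be fixed from the documents. Under the stated assumptions, full-thickness burns supply 1.2-16% of healing events. The power lost by an unstratified pooled test ranges from almost none to most of it, depending on how late surgery comes, how slowly these burns heal and the shape of the healing hazard. Restricting to the named depths, or stratifying by severity, kept power at about 75-85% in the simulated cases.

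**What to change.** Make the analysed and concluded populations match by one of two routes. The choice is the sponsor's.

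(a) **Restrict the primary comparison.** State in IV.F that the primary log-rank and Cox comparison uses burns in the partial and deep partial categories, fixed at baseline before allocation, with full thickness reported separately. Say which category an averaged score between categories enters (7.5 decides inclusion), and whether the category belongs to the patient or to the extremity. The cost is wording and about 1-16% of healing events under the assumptions above. Enrolment need not change.

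(b) **Keep all randomised burns.** Widen the hypothesis (in section I and where the background repeats it), Aim 1 and IV.G to all enrolled depths, and stratify the log-rank and Cox analyses by the severity categories used in randomisation. No events are lost, and the wording then agrees with the title, Aim 2 and section III. The cost is a broader claim, whose estimate could be diluted if the effect is absent in full-thickness burns. Averaged scores between categories still need a rule, because they define the strata.

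Severity is already scored and balanced in allocation, so neither route needs new data.
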